#### 2.5.3 Sleep Disturbances Post-Concussion

Sleep disturbances are reported in up to 72% of patients with mild, moderate, and severe TBI up to three years post-injury. Those TBI patients with sleep disturbances have longer inpatient hospital stays, a higher cost of rehabilitation, and a greater rate of functional disability. Current clinical practice guidelines advocate aggressive management of sleep hygiene after TBI to improve neurological symptoms and cognitive outcomes; however, the evidence behind this is lacking, and the neural mechanisms underlying sleep disturbances after TBI are unknown. Moreover, our current therapeutic options for sleep disturbances are less effective in patients with TBI-related sleep problems than with other sleep disorders. Preliminary data from our laboratory suggest that after LFPI, mice show significant sleep disturbances for up to 30 days post-injury compared to sham surgery controls, including more time sleeping during the active phase and increased sleep fragmentation (defined by an increased number of sleep-wake transitions and shortened average length of sleep and wake bouts). BCAA supplementation seems to attenuate some of these sleep disturbances after TBI.

### 2.5.4 Balance and Vestibular Impairments Post-Concussion

Balance or postural control is necessary in activities of daily living and sport. Balance requires the CNS to process and integrate afferent information from the visual, somatosensory (proprioceptive), and vestibular systems to then perform coordinated musculoskeletal responses. Abnormal static and dynamic balance is well described in survivors of TBI and altered postural dynamics is frequently found immediately after a concussive injury. Balance deficits usually resolve within 3 to 10 days after injury, however, they may be identified even years after injury in up to a third of patients and self-reported balance difficulty often correlates with persistent post-concussion symptoms. Instrumented testing devices are considered the gold standard of balance testing since they attempt to objectively measure balance. The computerized dynamic posturography (CDP) test as an objective means to assess balance by examining the response pattern to simultaneous, multimodal sensory stimulation.

### 2.5.5 Branched Chain Amino Acids

Branched chain amino acids are essential amino acids, meaning they cannot be synthesized *de novo* and therefore must be acquired through the diet. They are involved in numerous functions in the human brain including protein synthesis and energy production. A significant fraction of ingested BCAA's is not metabolized by the liver and passes directly into the systemic circulation, causing plasma concentrations to rise appreciably. BCAA's are important for protein metabolism throughout the body. They are transported into the brain by high affinity, low capacity transporters, located at the blood–brain barrier on capillary endothelial cells. Leucine enters the brain faster than any other amino acid, but valine and isoleucine also readily cross the blood-brain barrier.

Once in the brain, BCAA's are key amino acids involved in *de novo* glutamate (the major excitatory neurotransmitter in the CNS) synthesis, as approximately 50% of brain glutamate contains BCAA-derived nitrogen. Furthermore, *de novo* glutamate synthesis contributes approximately 40% of the releasable synaptic glutamate. It is believed that astrocytes remove released glutamate from the synaptic cleft, and amidate it to form glutamine for return to the neuron. This process, known as the glutamate:glutamine cycle, requires *de novo* glutamate synthesis to maintain sufficient presynaptic releasable neurotransmitter pools. If this process continued unabated, it would lead to a net transfer of nitrogen from astrocytes to neurons. Nature prevents this by shuttling BCAA's in the opposite direction (i.e., from the neuron to the astrocyte). Due to the intrinsic role for BCAA's in glutamate and subsequent GABA (the major inhibitory neurotransmitter in the mammalian CNS) synthesis, and the interrelationship between the glutamate:glutamine cycle and the presumed BCAA-dependent astroglial:neuronal nitrogen shuttle, changes in these three specific amino acids likely contribute to post-traumatic alterations in both hippocampal excitability and cognitive performance.

#### 2.6 Compliance Statement

This study will be conducted in full accordance with all applicable Children's Hospital of Philadelphia (CHOP) Research Policies and Procedures and all applicable federal and state laws and regulations. The investigators will perform the study in accordance with this

protocol, will obtain consent and assent, and will report unanticipated problems involving risks to subjects or others in accordance with CHOP's Institutional Review Board (IRB) Policies and Procedures and all federal requirements. Collection, recording, and reporting of data will be accurate and will ensure the privacy, health, and welfare of research subjects during and after the study.

# **3 STUDY OBJECTIVES**

The purpose of this study is to determine whether dietary administration of BCAA's shows evidence of improving the recovery of neurocognitive symptoms after concussion injury, and to determine which of several doses of dietary BCAA's shows the highest promise of efficacy.

8

# 3.1 Primary Objective

The primary objective of this study is to determine whether, compared to placebo treatment, administration of BCAA's, at one or more doses, after a concussion improves processing speed recovery at one or more time-periods post concussion. In the event that differences are observed, we will determine whether differences in processing speed between BCAA-treated and placebo-treated groups reflect differences in the maximum level of impairment and/or increases in the subsequent speed of improvement.

## 3.2 Secondary Objectives

The secondary objectives are to:

- Determine whether administration of BCAA's improves neurocognitive recovery compared to placebo for the cognitive domains of attention, learning, and working memory, and if so determine whether the results reflect differences in maximum levels of impairment or increases in subsequent speed of improvement.
- Evaluate whether BCAA supplementation improves clinical symptom resolution.
- Determine whether BCAA supplementation reduces the time to return to normal activities, specifically school or work, and participation in sports.
- Assess dose-related compliance of subjects with daily self-administration of BCAA's and with completion of study endpoints.
- Assess feasibility of enrolling potential subjects within 72 hours of concussion injury.
- Assess safety of BCAA supplementation in concussed patients.

# 4 INVESTIGATIONAL PLAN

## 4.1 General Schema of Study Design

The proposed study is a therapeutic exploratory clinical trial that will evaluate the effects of BCAA's on the magnitude and recovery of neurocognitive deficits following concussion injury.

## 4.1.1 Screening Phase

Physicians and advanced practice providers who have experience in diagnosing concussion, will identify potential subjects. The investigators and co-investigators will inform the groups of physicians who will be referring patients to the study (e.g. CHOP and Penn Sports Medicine, CHOP and HUP Emergency Medicine) about the study procedures and their role in referring patients via email and presentations at local conferences. For these groups of physicians, the diagnosis of concussion is informed by the commonly published guidelines for the diagnosis of concussion. The most widely used is the Consensus Statement on Concussion in Sport: The 5th International Conference on Concussion in Sport, Berlin, October 2016. Others societies and professional organizations including the American Academy of Neurology, American Academy of Pediatrics, and the American Medical Society for Sports Medicine have publications which contain similar diagnostic guidelines. A potential subject is a patient who has had a concussion, as diagnosed by a physician, within the prior 72 hours, is between the ages of 11 and 34, and, in the opinion of the physician, has capacity to consent to participate in the study. Verification of the diagnosis of concussion will be made by obtaining written documentation from the referring physician or advanced practice provider. This documentation may come in several forms including a copy of a clinic note, a copy of an ED or hospital note, summary statement or discharge document, or an email sent directly from the physician confirming the diagnosis. This documentation will be reviewed by a physician from the study staff to confirm that the patient was diagnosed by a qualified physician or advanced practice provider to have a concussion. The source document and documentation of the PI's review and confirmation of the diagnosis will be maintained in the subject's file.

Potentially eligible subjects will be referred to the study coordinator and subsequently screened by a study staff member using the protocol inclusion and exclusion criteria during an in-person interview. Post-menarchal females will have a urine pregnancy test performed, or documented as negative within 72 hours prior to enrollment. Informed consent and, if applicable, parental/guardian consent and child assent, will be obtained prior to any study related procedures being performed. If enrolled, subjects will be randomized to receive one of four different dose levels of BCAA's or placebo.

## 4.1.2 Study Treatment Phase

Subjects enrolled in the trial will be randomized to receive either oral BCAA's at doses of 7.5, 15, 22.5, or 27 g BID or an oral placebo BID for a total of 21 days. Subjects will complete five on-line computerized assessments daily:

- 1. Axon Sports Computerized Cognitive Assessment Tool
- 2. Clinical symptom checklists (Appendix 1)

- 3. Cognitive and physical activity assessments (Appendix 2)
- 4. Sleep assessment (Appendix 3)
- 5. Drug accountability assessment (Appendix 4)

Subjects will wear an actigraphy monitor for the duration of the trial to assess sleep patterns. Computerized Dynamic Posturography may be conducted at 3 time points (days 0-4, 5-9, and 12-16) during the study treatment phase.

## 4.2 Allocation to Treatment Groups and Blinding

The study biostatistician, [name], will generate a randomization schedule for implementation in the randomization module of the study database system. The randomization scheme will be based on an equal allocation of each of the possible doses or placebo, and stratified based on sex. The randomization schedule is uploaded into the data management system (DMS) and provided to the Investigational Drug Service (IDS). The IDS will use the randomization schedule to prepare kits of BCAA doses or placebo for distribution. Upon confirmation of eligibility, the DMS will provide study personnel with a number that is then given to the IDS and corresponds to the kit number to be distributed. All study team members will be blinded to treatment assignment. The Database Administrator will have access to the link between the kit number and the treatment arm and will provide this information to the Investigational Drug Service (IDS) so that kits are prepared according to this scheme. BCAA and placebo treatment kits will appear identical.

## 4.3 Study Duration, Enrollment and Number of Sites

## 4.3.1 Duration of Study Participation

The study duration per subject will be up to 22 days, with up to 1 day screening and up to 21 days in the treatment phase.

# 4.3.2 Total Number of Study Sites/Total Number of Subjects Projected

The study will be conducted through the Children's Hospital of Philadelphia and the Hospital of the University of Pennsylvania. Recruitment will stop when 50 subjects who are evaluable for efficacy are enrolled. A subject who is evaluable for efficacy is one who completes the study up until at least day 10 of the study. It is expected that approximately 72 subjects will be enrolled to produce 50 such subjects. All subjects who enroll and receive study medication will be evaluable for safety.

## 4.4 Study Population

## 4.4.1 Inclusion Criteria

- 1) Males and females, ages 11 34 years, of any race.
- 2) Weight at least 40kg.
- 3) Subjects who had a concussion, as diagnosed by a qualified physician or advanced practice provider, within the 72 hours prior to enrollment.
- 4) Ability to have daily email and internet access.

- 5) Post-menarchal females must have a negative urine pregnancy test and must use an acceptable method of contraception including abstinence, a barrier method (diaphragm or condom), Depo-Provera, or an oral contraceptive for the duration of the study.
- 6) Subjects must, in the opinion of the referring physician, have the capacity to provide informed consent, defined by: 1) the ability to communicate; 2) the ability to assess their understanding of the treatment; 3) the ability to understand the risks and benefits of the treatment; and 4) the ability to understand the risks and benefits of not embarking on the treatment.
- 7) Informed consent by the subject, or for subjects <18 years old both informed consent by a parent/guardian and child assent.

#### 4.4.2 Exclusion Criteria

- 1) Witnessed seizure at the time of injury or penetrating head injury.
- 2) Prior concussion or TBI within 90 days.
- 3) Concussion or TBI severe enough to require admission to an intensive care unit for observation or intervention, specifically for the traumatic brain injury.
- 4) Previous history of TBI or concussion requiring admission to the hospital, disabling stroke, epilepsy, brain tumor, neurodegenerative condition, or psychiatric disease.
- 5) Subjects taking neurological or psychoactive medications as a regular daily prescription medication (e.g. stimulants, antidepressants, anticonvulsants, benzodiazepines, etc.).
- 6) Known history of maple syrup urine disease or known family history of maple syrup urine disease.
- 7) Any investigational drug use within 30 days prior to enrollment.
- 8) Allergy to FD&C Red #40 (red dye 40) or Sucralose.
- 9) Lactating females.
- 10) Parents/guardians or subjects who, in the opinion of the investigators, may be noncompliant with study schedules or procedures.

Subjects that do not meet all of the enrollment criteria may not be enrolled. Any violations of these criteria must be reported in accordance with IRB Policies and Procedures.

### **5 STUDY PROCEDURES**

#### 5.1 Screening Visit

- Informed consent
- Review of inclusion and exclusion criteria
- Urine pregnancy test (for post-menarchal females only)

### 5.2 Study Treatment Phase

At the start of the treatment phase at Visit 1, the study coordinator or study staff member will obtain demographic information, a concussion history and measure height and weight. The study drug will be dispensed in 42 bottles at the time of enrollment. The assessments during the study treatment phase will be web-based and completed daily through the study website:

- 1. Axon Sports Computerized Cognitive Assessment Tool
- 2. Clinical symptom checklists (Appendix 1)
- 3. Cognitive and physical activity assessments (Appendix 2)
- 4. Sleep assessment (Appendix 3)
- 5. Drug accountability assessment (Appendix 4)

Subjects will wear an actigraphy monitor for the duration of the trial to assess sleep patterns. Subjects will have the option to complete computerized dynamic posturography (CDP) measured on visits 1, 2, and 3, which correspond to study, days 0-4, 5-9 and 12-16. If enrollment occurs on a Saturday or Sunday, CDP can be conducted the following Monday or Tuesday. The actigraph monitor will be downloaded during the CDP visits, and after being returned at the conclusion of the study (Visit 4, Days 22-24). Subjects will be screened for drug accountability via a urine assay on visits 2 and 3, which correspond to study days 5-9 and 12-16.

We recognize that the data collection we are requesting of subjects may be onerous, and return visits for study procedures are a significant burden for subjects. Early subject recruitment has demonstrated issues with consistent compliance with study procedures. Therefore, we will institute graduated rewards for continued participation during the study. Using a token economics approach, study subjects will be rewarded by text- or email-based reinforcement for each data entry completed, including visual representations of compliance to serve as reminders/motivators for sustained compliance. These will graphically and/or by text show how close they are to meeting the 3-day-in-a-row and 7-day-in-a-row endpoints, which will have associated monetary incentives (see subject payment section).

Visit	Purpose Main Procedures		Duration
Visit 1, Day 0	Screening	Informed consent Review inclusion/exclusion criteria Urine pregnancy test (post-menarchal women only)	15 minutes
Visit 1, Day 0	Orientation Start Study Drug	Orientation to study & study website Demographics & concussion history Baseline compliance urine test	2 hours

04/06/2018 V 0.16

		Computerized balance testing (optional)* Distribute actigraphy sleep monitor Distribute study drug	
Days 0-21	Daily assessments via study website	Computerized cognitive testing Clinical symptom checklists Cognitive & physical activity assessments Sleep assessment	15 minutes
Visit 2, Day 5-9	Routine Visit	Computerized balance testing (Optional) Compliance urine test	20 minutes
Visit 3, Day 12-16	Routine Visit	Computerized balance testing (Optional) Compliance urine test	20 minutes
Visit 4, Day 22-24	End of Study	Return used and unused drug bottles Return actigraphy monitor	10 minutes

\* - If enrollment occurs on a Saturday or Sunday, balance testing can be conducted the following Monday or Tuesday.

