We note that with five treatment groups and 21 time points, there are a very large number of possible hypothesis tests that can be carried out with these data. If all of these tests were carried out without adjusting for multiple comparisons, we would undoubtedly find spurious associations. On the other hand, adjusting for large numbers of multiple comparisons substantially reduces the statistical power of a study. By focusing our testing for the primary efficacy analysis on three key periods where we adjust for a limited number of tests, we balance the need for a rigorous statistical testing procedure with a need to maintain statistical power.

An analysis of the Day 1-2, 15-18 and 19-21 data will follow the same format, but will be considered secondary and will not be formally corrected for multiple testing. In addition to hypothesis testing, we will estimate and plot means and confidence intervals for each group at each time point. This analysis will guide the recommendation for dose levels and evaluation times for the primary analysis in future efficacy studies.

With concerted efforts from our study coordinators and study staff we are hopeful that we can maintain excellent compliance throughout the study. In particular we expect good compliance early in the study when patients are highly motivated to feel better and return to school, work and play. However, we allow that some patients may have difficulty with compliance due to their injury, or become non-compliant once their symptoms improve. As part of this feasibility study, we will explore patterns of missing data, in particular how they may relate to the observed response (e.g. more missing data in those subjects who show better or worse processing speed) to compliance (e.g. more missing data in subjects who regularly fail to consume their supplements) and to demographics e.g. gender, age. This information will be valuable in planning future efficacy trials, and will guide our efforts to adjust for missing data. For example if the probability of missing data is associated with outcome, then non-ignorable missing data methods will be needed, whereas missing at random assumptions will be valid if the missing data can be explained by covariate information.

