#### 7.3.3 Analysis of Secondary Endpoints

Secondary endpoints, including clinical symptoms such as the posturography and sleep assessments, and the learning, attention and working memory components of the neurocognitive battery will be modeled using a similar approach as described above for the primary efficacy analysis (Section 7.3.2), with the goal of assessing differences between groups over time, after adjustment for age differences. We will assess the distribution of the outcome and either use a transformation to achieve approximate normality or use a generalized mixed effects model. Time to event outcomes (e.g. time to return to school or sports participation) will be modeled using a Cox proportional hazards model. We will secondarily adjust our primary models for body mass index (BMI) and compliance to obtain information on whether individuals with lower BMI, and presumably higher BCAA/kg dosing have better outcome.

We will also monitor compliance including adherence to treatment and daily completion of neurocognitive testing. It is of interest to determine whether there are differences in compliance among the dosage groups versus placebo whether compliance decreases as a function of time, and whether compliance differs among groups over time. Adherence to treatment is measured in terms of number of bottles of consumed per day (0, 1, or 2) and will be modeled as an ordinal outcome. Adherence to treatment will be assessed using generalized estimating equations (GEE) models as we have repeated measures on adherence for each subject across all time points in the study and are primarily interested in differences between groups. In particular we anticipate that with regular prompting and encouragement, subjects will consistently complete their neurocognitive functioning tests up until about 10 to 14 days into the study. We anticipate that compliance may begin to decrease around the 10 to 14 day point as subjects begin to feel better and return to their normal routines. Assessment of compliance will be key information needed to design the anticipated pivotal trial of subsequent research studies.

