## 10.7 Payment to Subjects/Families

Subjects will receive a possible total of \$100 for participation in this study. Amount received will depend on compliance with study procedures and will be offered in a graduated schema to encourage ongoing participation. Payment will be placed on a reloadable CHOP-issued card and money added throughout the study. Subjects will receive \$20 on the card at the time of visit 1. Each day that they input all required study data will add \$1, with a bonus of \$2 each time 3 days in a row are met and \$5 each time 7 days in a row are met, for a possible total of \$50 if all 21 days of data are entered completely. \$10 will be added for each in-person research visit that they attend (possible total of \$30 for 3 visits)..

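### Compliance-linked rewards began part-way through the study, but no before/after summary of compliance or missing data is specified

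*Combined protocol and SAP*

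**What the plan says.** Section 5.2 reports a problem and a response to it: "Early subject recruitment has demonstrated issues with consistent compliance with study procedures. Therefore, we will institute graduated rewards for continued participation during the study". The scheme has two parts. One is messages: "study subjects will be rewarded by text- or email-based reinforcement for each data entry completed". The other is money, set out in Section 10.7: $1 for each day with all required data entered, $2 for each run of 3 days and $5 for each run of 7 days. Section 8.1.4 adds twice-daily reminder messages that also reward subjects who have documented taking their drink.

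Compliance is a secondary objective (3.2) and a secondary endpoint (7.2). Section 7.3.3 models bottles per day (0, 1 or 2) as an ordinal outcome by GEE. It asks whether compliance differs between the dose groups and placebo, and also "whether compliance decreases as a function of time, and whether compliance differs among groups over time". It then gives the purpose: "Assessment of compliance will be key information needed to design the anticipated pivotal trial".

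For missing data, Section 7.3.2 says "we will explore patterns of missing data, in particular how they may relate to the observed response", and adds compliance with the supplement and demographics such as gender and age.

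Section 7.3.1 deals with another mid-study change. Subjects who received the 60 g/d top dose stay in one group with those on 54 g/d, and a subgroup analysis compares the two.

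**The concern.** The rewards were brought in to change the quantities that Section 7.3.3 measures. Payment depends on complete daily entry, which includes the cognitive tests and the drug accountability form. The run bonuses encourage unbroken participation, and Section 7.3.3 expects compliance to begin falling at about days 10 to 14. Both the level of compliance and its shape over study days could therefore differ before and after the scheme began.

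None of the planned analyses carries a term, stratum or separate table for reward period. Time in Section 7.3.3 means study day, not calendar period. Followed as written, the analysis would give one overall level and one time course from subjects under two sets of incentives. A pivotal trial will run under one set. The missing-data work has the same gap: Section 7.3.2 would accept a missing-at-random assumption where covariates account for the missingness, and reward period is an obvious candidate covariate.

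**Working it through.** **Figures the plan states**

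- Evaluable yield (4.3.2, 7.4): 50 of 72 = 69.4%, a loss of 30.6%. Check: 50 / 0.694 = 72. The plan does not say which incentive regime this yield assumes.
- Payments (10.7): 21 × $1 + 7 × $2 + 3 × $5 = 21 + 14 + 15 = $50 tied to daily entry. Adding $20 at visit 1 and 3 × $10 for visits gives $100. The total agrees, and half of it depends on daily compliance.
- No compliance rate, reward start date or number enrolled before the rewards appears in the documents, so nothing further can be computed from them alone.

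**The sections side by side**

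| Mid-study change | Arms touched | Earlier subjects kept | Before/after split planned |
|---|---|---|---|
| 60 to 54 g/d (7.3.1) | one | yes | yes |
| Graduated rewards (5.2, 10.7) | all | no exclusion stated | no |

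**What mixing does to a rate**

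Let w be the share enrolled before the rewards. The overall rate is w × p(before) + (1 − w) × p(after). It lies strictly between the two whenever both periods have subjects and the rates differ.

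The following is an illustration only. The evaluable rates of 60% before and 80% after, and every value of w, are assumptions. Enrolment is the number needed for 50 evaluable subjects, 50 / rate, rounded up.

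| w | Overall rate | Points below the after rate | Enrolment implied |
|---|---|---|---|
| 10% | 0.06 + 0.72 = 78% | 2 | 65 |
| 25% | 0.15 + 0.60 = 75% | 5 | 67 |
| 50% | 0.30 + 0.40 = 70% | 10 | 72 |
| 75% | 0.45 + 0.20 = 65% | 15 | 77 |

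The rewarded rate itself would imply 50 / 0.80 = 63, and the unrewarded rate 50 / 0.60 = 84. Using the overall rate would over-enrol a rewarded trial and under-enrol an unrewarded one. That the 50% row matches the plan's 72 is coincidence.

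**What a split can support**

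Taking the rate at 69.4%, the 95% half-width is 1.96 × √(0.694 × 0.306 / n). That is 10.6 points for n = 72, 15.0 for n = 36 and 21.3 for n = 18. Power to detect 60% against 80% between periods is about 46% with 36 and 36 subjects, and about 40% with 18 and 54. A formal before/after test would be weak, so the split should be descriptive.

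**The case against.** The strongest reply is that nothing here is excluded. Section 7.3.3 is a short outline and nowhere says that compliance will be reported as one pooled rate. The missing-data factors in Section 7.3.2 are given as examples, and the study calls itself a feasibility study. A table by enrolment period could be added at any time. That is right as far as it goes: the gap is an unspecified summary, not a wrong method. But the split for the dose change shows that the plan writes such summaries down when it sees the need.

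The second reply is that the compliance objective is dose-related, and the reward scheme is described without distinction between arms. This stands. Arms remain randomised within each period, so comparisons of dose with placebo are not at issue. What is left is the absolute level of compliance, its course over study days and the evaluable yield.

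Three stronger readings are tempting, and the documents do not support them:

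- A reader might infer that the overall estimate will represent neither regime. If only a few subjects came before the rewards, it is in practice the rewarded rate.
- A reader might infer that payment itself was new. Section 10.7 gives only current amounts, and no section says what was paid before. What Section 5.2 shows as new is the graduated link to compliance.
- A reader might infer that the pivotal trial will be mis-sized by a definite percentage. Every rate behind such a figure would be assumed, and Section 7.3.3 says only that compliance will inform that trial's design.

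**Conclusion.** The point holds as a minor, nearly free improvement. The plan introduces compliance-linked rewards in response to poor early compliance, names compliance as a planning input, and specifies no summary that separates subjects by reward period, although it does so for its other mid-study change.

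The size is unknown. It depends on the share enrolled before the rewards and on how far they changed behaviour, and the documents give neither. On the assumed 60% and 80%, the overall rate would be 2 to 15 points below the rewarded rate for early shares of 10% to 75%. It would be near zero if very few enrolled earlier, and zero if the rewards changed nothing. The conclusion assumes that earlier subjects stay in the compliance analyses. Section 7.3.1 supports this by keeping those on the earlier top dose, and no section removes anyone on this ground. The error rates of the primary tests and the randomised comparisons are untouched.

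**What to change.** In Section 7.3.3:

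1. Record the date the rewards began and the number enrolled before it, and state how subjects in follow-up on that date are classified.
2. Report adherence, test completion and the evaluable (Day 10) rate by reward period with confidence intervals, as a descriptive summary.
3. Add a reward-period indicator to the adherence GEE as a sensitivity analysis.
4. State that planning for the pivotal trial will use the period whose incentives match that trial.

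In Section 7.3.2, include reward period among the factors examined for missing data.

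The cost is a few sentences and a start date that the study team should be able to supply; no new subject data are needed. The price is precision, since fewer subjects stand behind each rate. The contrast is also not randomised, and it may overlap in time with the change in the top dose's concentration, so it should not be read as a test of whether the rewards worked.
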